### 6.6 Correlative Studies

# 6.6.1 Nanostring Assays of Paired Samples

Morphologic predictors of response include expression of PD-LI, an interferon gamma target indicative of an active inflammatory response to tumor, and the presence of tumor infiltrating CD8 T cells, dendritic cells, and NK cells of particular phenotypes. The therapeutic hypothesis for this study centers on the possibility that treatment with ivosidenib will either induce or augment an antitumor inflammatory response, and/or will induce production of neoantigen presenting MHC class I in the

# tumor.

The primary goal of the biopsy analysis is to determine whether the tumor has sustained an infiltration by innate and adaptive immune cells, and/or increased tumor expression of antigen expression apparatus such as components of MHC Class I, consistent with the therapeutic hypothesis. The secondary goal is to determine whether either the baseline level of inflammatory infiltrate or the level induced by ivosidenib treatment is predictive of immediate an extended response to the combination of ivosidenib with nivolumab.

The primary assays for analysis of the paired biopsies are the Nanostring 10 360 assay, an extensively validated transcript profiling assay used for semi-quantitative cell enumeration and transcriptional response in biopsies (Danaher, Warren et al. 2017), as well as immunofluorescence based direct enumeration of immune cells and their spatial co-localization. Assay is subject to change based on available technologies at the time of analysis.

The primary hypothesis for statistical analysis of the paired biopsies is to accept or reject the hypothesis that the tumor inflammation signature (TIS, or T cell-inflamed GEP), a function calculated from the abundance of 18 transcripts detected in the sample (Table below), has changed in the tumor due to therapy. This function is highly correlated with anti-PDI antibody treatment outcome (Ayers, Lunceford et al. 2017).

TIGIT	PD-LI	PSMBIO	STATI
CD27	CXCR6	IDO1	HLADRBI
CD8A	CMKLRI	CXCL9	HLAE
PD-L2	NKG7	HLADQAI	
LAG3	CCIS	CD276	

# Table 4: Eighteen Component Transcripts of Tumor Inflamed Signature (TIS) Score

Several outcomes may be envisaged:

- Ivosidenib causes an increase in TIS in a subset of patients and that increase is associated with an increase in PFS.
- Baseline TIS is associated with PFS, and changes induced ivosidenib treatment are not associated with changes in PFS.
- Ivosidenib does not affect TIS in any patient.

# 7.0 Safety and AEs Assessing, Recording, and Reporting

AEs will be monitored throughout the study (once participants have received study drug); SAEs that are assessed as related to study treatment that occur> 100 days post treatment also are to be reported. All AEs should be monitored until they are resolved or are clearly determined to be due to a participant's stable or chronic condition or intercurrent illness(es).

### Adverse Event Reporting Period

Investigators will seek information on AEs at each participant contact, as outlined below. All AEs, whether reported by the participant or noted by study personnel, will be recorded in the participant's medical record.

After informed consent has been obtained but prior to initiation of study drug, only SAEs caused by a protocol-mandated intervention should be reported (e.g., SAEs related to invasive study procedures such as biopsies).

After initiation of study drug, all AEs and SAEs regardless of attribution will be collected at every visit until 100 days following the last administration of study treatment or until study discontinuation/termination or until initiation of subsequent anticancer therapy, whichever occurs first. Participants will be assessed at the Follow-up Visit to determine if any new AEs have occurred. After this period, Investigators should report only SAEs that are considered to be related to study treatment.

All Serious Adverse Events (SAEs) that occur following the participant's first does of study treatment through 100 days of discontinuation of dosing must be reported to according to section 7.3, whether related or not related to study drug.

Following the participant's first dose of study treatment, all SAEs, whether related or not related to study drug, are collected, including those thought to be associated with protocol-specified procedures. The investigator should report any SAE occurring after these aforementioned time periods, which is believed to be related to study drug or protocol-specified procedure.

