Participants may continue with their assigned study treatment until disease progression, development of unacceptable toxicity, confirmed pregnancy, death, withdrawal of consent, the participant is lost to follow-up, or the Lead Principal Investigator (PI) ends the study, whichever occurs first. For participants who are determined to be on ivosidenib upon radiographic disease progression and demonstrate clinical benefit, treating investigators, with consult from the Lead PI, may keep the participants on ivosidenib after the disease progression.

**Post-Treatment Follow-up Visit:** A Post-Treatment Follow-Up Visit for safety will occur 28 days (no more than 33 days) after the last dose of study drug. Every effort must be made to perform protocol-specified evaluations unless consent to participate in the study is withdrawn. Assessments to be performed at the Follow-up Visit are included under study assessments. If a participant's dose is interrupted for 28 days and then the participant discontinues study participation, the EOT Visit will serve as the Post-Treatment Follow-up Visit.

**PFS Follow-up:** Participants who discontinue study treatment for reasons other than disease progression or withdrawal of consent will be followed in PFS follow-up (every 8 weeks through week 48, and every 8 weeks thereafter) until documented disease progression, death, or the initiation of new cancer therapy. If a participant begins a new anticancer therapy during PFS follow-up, information on the new anticancer therapy will be collected.

**End of Study:** End of study is defined as the point in time when all participants have died, withdrawn consent, or been lost to follow-up.

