# 4.4.1 Withdrawal from Study Treatment

Participants may discontinue or be discontinued from study treatment at any time. In this situation, a participant without documented progressive disease by the treating investigator should be followed for tumor assessments until the development of progressive disease and/or survival. Participants will be discontinued from study treatment for the following reasons:

- Grade 4 QTcF prolongation.
- Disease progression (participants who are, in the opinion of the treating investigator, benefiting from treatment [e.g., slow progression or immune-related response evaluation] may be allowed to continue on study treatment)
- Severe or unacceptable toxicity
- Death
- Lead Investigator decision
- Subject decision to withdraw from treatment
- Protocol violation: non-adherence to study treatments as required for evaluability (detailed in section 8.1.1) or other protocol requirements.
- Confirmed pregnancy (study therapy should be immediately interrupted based upon a positive urinary human chorionic gonadotropin [hCG] test, and permanently discontinued if confirmed by a serum -hCG test)
- Lost to follow-up

All AEs should be followed until resolution or for a period of 28 days from the last dose of study treatment, whichever is shorter. If the participant withdrew from treatment because of an AE, every

effort must be made to perform protocol-specified safety follow-up procedures. All SAEs that occur up to 100 days post last dose of nivolumab must be reported to BMS World Wide Safety.

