### 4.4.2 Study Participation Termination

Participants who discontinue treatment without disease progression or death will continue to be followed for PFS every 8 weeks after the EOT Visit (±5 days) until disease progression, death, start of subsequent anticancer therapy, or withdrawal of consent until 6 months after the last enrolled patient begins treatment. Participants will be terminated from the study for the following reasons:

- Death
- Withdrawal of consent for follow-up
- Loss to follow-up
- Termination of the study

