# 6.0 Study Processes and Assessments

### 6.1 Schedule of Events

Table 3 provides the schedule of assessments for this study. Pre-screening or screening for IDH1 will occur via CLIA certified standard of care sequencing. After obtaining written informed consent for the study overall, all participants will undergo Screening procedures to determine eligibility within 28 days prior to the start of study treatment on C1D1. Participants are to attend study center visits as outlined in the Schedule of Assessments (Table 3).

An EOT Visit will be conducted as soon as possible after discontinuing study treatment (within 5 days of last dose of study treatment, if study drug dosing has not been delayed); in addition, participants are to attend a Follow-up Visit 28 days (no more than 33 days) after the last dose of study treatment for final safety assessments. If a participant's dose is held and it is subsequently decided to discontinue treatment, the EOT Visit should be conducted as soon as possible, within 28 days (and no more than 33 days) after the last dose of study treatment for final safety assessments.

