- Female participants with reproductive potential must have negative serum pregnancy testing within 24 h prior to the initial administration of study drug, then every 4 ± 1 week, or a negative confirmation from an obstetrician in case of equivocal serum pregnancy results. Females of reproductive potential are defined as sexually mature women who have not undergone a hysterectomy, bilateral oophorectomy, or tubal occlusion or who have not been naturally postmenopausal (ie, who have not menstruated) for at least 24 consecutive months (ie, have not had menses at any time in the preceding 24 consecutive months).
-  ctDNA to be collected C1D1, C1D15, C3D1, C4D1 (time of pt response assessment) and at time of progression. PBMCs to be collected C1D1, C1D15, C2D1, C3D1, C4D1 (time of pt response assessment) and at time of progression.

Germline DNA to be collected C1D1

Serum to be drawn C1D1, C1D15, C2D1, C3D1, C4D1 (time of pt response assessment) and at the time of progression.

Modification for 2-HG levels: Drawn on C1D1 (as baseline), at 1 month (C2D1), 3 months (C4D1) and at time of disease progression

Submit all required materials (eligibility checklist, source documentation, and signed consent form) to confirm eligibility and required pre-study procedures to the CRA a minimum of 48 h prior to the participant's scheduled therapy start date. Full details listed in Registration Procedures

Note that nivolumab will be dosed Q28 days via IV infusion, while ivosidenib will be continuous PO daily dosing

After cycle 3 (i.e., from C4 onwards), study visits will be monthly.

-  SAEs occurring within 100 days post last study drug dose must be reported to BMS World Wide Safety and Agios
-  Specific imaging modalities detailed under section 6.5 (Efficacy Assessments)
-  As clinically indicated
-  See Section 1.3.4 for research blood draw time points
-  See Section 6.4.3 Safety Laboratory Assessments

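### Safety events must be captured to day 100 after the last dose, but a participant who stops for progression has no scheduled contact after the day 28 to 33 visit, so late SAEs and deaths can be missed

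*Combined protocol and SAP*

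**What the plan says.** **What must be captured.** The Adverse Event Reporting Period text in section 7.0 states that "all AEs and SAEs regardless of attribution will be collected at every visit until 100 days following the last administration of study treatment". The sentence goes on to close the window early: "or until study discontinuation/termination or until initiation of subsequent anticancer therapy, whichever occurs first". A separate paragraph in 7.0, and section 7.2.2, require every SAE to day 100 to be reported and name no stop at new therapy. Footnote 8 of Table 3 does the same: "SAEs occurring within 100 days post last study drug dose must be reported to BMS World Wide Safety and Agios". Section 4.4.1 repeats the SAE duty, counting the 100 days from the last nivolumab dose. Section 8.2.2 defines the on-treatment death listing as running to 100 days after the last dose.

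**When participants are seen.** Section 3.1: "A Post-Treatment Follow-Up Visit for safety will occur 28 days (no more than 33 days) after the last dose of study drug". Section 6.1 treats this visit as the last one for safety: "participants are to attend a Follow-up Visit 28 days (no more than 33 days) after the last dose of study treatment for final safety assessments". Later contacts are restricted in section 3.1: "Participants who discontinue study treatment for reasons other than disease progression or withdrawal of consent will be followed in PFS follow-up". Section 4.4.2 agrees: "Participants who discontinue treatment without disease progression or death will continue to be followed for PFS every 8 weeks after the EOT Visit".

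**What else bears on it.** Section 7.4.2 has participants told, when they stop treatment, to report later AEs that their own physician thinks may be related. Section 8.2.2 restricts the AE summaries, including the SAE summary, to events up to 28 days after the last dose.

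**The concern.** Collection in section 7.0 is tied to visits and participant contacts, so a window can be filled only if contacts fall within it. For a participant who permanently stops both drugs because of progression, the calendar has none after day 33. Progression is not among the reasons for leaving the study in section 4.4.2, so the 100-day SAE duty still applies to that participant.

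Two things are at stake. One is complete SAE reporting to day 100. The other is the 100-day death listing. PFS follow-up ends at progression and no survival visit is scheduled, so no planned contact establishes vital status at day 100 for these participants. How actively late events are sought also depends on why treatment stopped.

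**Working it through.** The plan states no figure for this gap, so there is none to reproduce. The check compares the required window with the latest scheduled contact, by reason for stopping.

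**Inputs**
- Window: 100 days after the last dose (7.0, 7.2.2, Table 3 footnote 8, death listing in 8.2.2).
- Last safety visit: day 28, at latest day 33 (3.1, 6.1).
- PFS follow-up: every 8 weeks after EOT, ±5 days, for participants without progression only (3.1, 4.4.2).
- EOT: day 0 to 5 if dosing was not delayed (6.1), and up to day 33 after a dose hold (3.1).
- Accrual goal: 35 (8.0).
- Share stopping for progression, for scale only: 19 of 25 discontinuations in the earlier ivosidenib cholangiocarcinoma cohort (1.4.3.1).

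**Stopped for progression**
- Safety visit on day 33: 100 − 33 = 67 days without scheduled contact.
- Safety visit on day 28: 100 − 28 = 72 days.
- Counted from the last nivolumab infusion, as in 4.4.1, the gap is shorter. If the last ivosidenib dose ends a 28-day cycle, it falls 27 days after the infusion. The safety visit is then 27 + 28 = 55 to 27 + 33 = 60 days after the infusion, leaving 40 to 45 days. If ivosidenib continues alone beyond nivolumab's one-year limit, the gap on this count is shorter still or absent.

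**Stopped for another reason, without progression**
- First PFS visit: 0 + 56 − 5 = day 51 to 5 + 56 + 5 = day 66.
- Second PFS visit: 0 + 112 − 5 = day 107 to 5 + 112 + 5 = day 122.
- With EOT as late as day 33, the first PFS visit moves to 33 + 56 ± 5 = day 84 to 94, still within the window.

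These participants therefore have about one visit between day 34 and day 100. With an undelayed EOT, another follows soon after and can look back. This lasts only until they progress or start new therapy.

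**Scale, by assumption**
- Affected participants: 19/25 = 0.76, and 0.76 × 35 = 26.6, about 27. For a share of 50 to 90%: 17.5 to 31.5.
- Let q be the probability of at least one reportable event on days 34 to 100. The documents give no value for q. The expected number with an event that no visit solicits is 35 × share × q:

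| Share stopping for progression | q = 5% | q = 10% | q = 20% |
|---|---|---|---|
| 50% | 0.9 | 1.8 | 3.5 |
| 76% | 1.3 | 2.7 | 5.3 |
| 90% | 1.6 | 3.2 | 6.3 |

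- With 27 participants and q = 10%, P(at least one) = 1 − 0.9^27 ≈ 0.94.

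These are upper limits on loss. They allow nothing for passive reporting, for the all-AE window closing at new therapy, or for treatment continued beyond progression.

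**The case against.** The strongest reply has four parts.

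1. **Planned rates are not biased.** A reader might infer that late AE and SAE rates will come out too low and vary with tumor outcome. The documents do not support that. The AE and SAE summaries in 8.2.2 stop at 28 days after the last dose, and every participant has the day 28 to 33 visit whatever the reason for stopping. No planned rate uses days 34 to 100. This stands in full. The DLT rule looks only at Cycle 1, and the primary endpoint is untouched.

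2. **For AEs in general the window often closes early by design.** Participants who progress are likely candidates for new therapy, which ends all-AE collection under 7.0. This stands for non-serious AEs, so 67 days is a ceiling for them. It does not dispose of SAEs: the sentence containing the cut-off names them too, but the later paragraph of 7.0, section 7.2.2 and Table 3 footnote 8 set no such limit.

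3. **Other routes exist.** Investigators must record what they learn at any contact and report SAEs whether or not a visit is due, and participants are told to report related events (7.4.2). It would therefore be wrong to say that late events are missed, or that there is no planned way to record them. But these routes are passive, and the participant's route covers only events thought related, while the SAE duty applies whatever the cause. An SAE treated elsewhere and thought unrelated may never reach the site.

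4. **The contrast between groups is one of degree.** Participants who stop without progression have about one PFS visit in the interval, not full coverage. Participants treated beyond progression (3.1, 4.4.1, 5.5.2) keep their visits until their final dose. Both points stand.

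A reader might also take the 100-day window to exist for late nivolumab effects. The documents tie the SAE window to the last nivolumab dose in 4.4.1 but give no reason for its length, so this point does not rest on that.

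**Conclusion.** The mismatch holds, within limits. For participants who permanently stop because of progression, the plan requires SAE reporting and a death listing to day 100 but schedules no contact after day 28 to 33. As many as 67 days after a day-33 visit (72 after a day-28 visit) rely on passive reporting. The interval is shorter for non-serious AEs if new therapy starts, and shorter when counted from the last nivolumab infusion. Late SAEs and deaths can be missed, more easily than in participants who stopped without progression.

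About 27 of 35 participants would be affected, with about 1 to 5 having an event that no visit solicits. This assumes that the 76% share from a single-agent cholangiocarcinoma cohort carries over, that all 35 eventually stop treatment, and that the late-event risk is 5 to 20%. It is an upper limit on loss. The effect is confined to 100-day SAE reporting and the death listing, and it is worth correcting because the remedy is small.

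**What to change.** Add to sections 3.1 and 7.0 and to Table 3 one telephone or record-review check at day 100 after the last dose, for every consenting participant not in PFS follow-up, including those who have started new therapy. It should record SAEs and vital status for all of them, and AEs where the all-AE window in 7.0 is still open. Participants who leave PFS follow-up before day 100 would then be covered too.

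In the same amendment:
- Make 7.0 consistent on whether SAE collection stops at new therapy.
- Reconcile the rules on how long an AE is followed. Section 4.4.1 says "All AEs should be followed until resolution or for a period of 28 days from the last dose of study treatment, whichever is shorter", whereas the opening of 7.0 and section 7.4.1 follow AEs until they resolve or are judged stable, and the reporting period in 7.0 runs to day 100.

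The cost is protocol and calendar wording plus one call or record check per affected participant: about 27 at the 76% share, and about 18 to 32 at 50 to 90%. No clinic visit or procedure is added, and the 28-day summary tables need no change on this account.

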### 7.1 Definition of AEs

### 7.1.1AEs

An AE (also referred to as an adverse experience) is any untoward medical occurrence associated with the use of a drug in humans, whether or not considered drug related. An AE can therefore be any of the following:

Any unfavorable and unintended sign (e.g., an abnormal laboratory finding), symptom, or disease temporally associated with the use of a drug, whether or not considered related to the drug.

Any new disease or exacerbation of an existing disease (a worsening in the character, frequency, or severity of a known condition).

Recurrence of an intermittent medical condition (eg, headache) not present at baseline.

Any deterioration in a laboratory value or other clinical test (eg, ECG, X-ray) that is associated with symptoms or leads to a change in study treatment or concomitant treatment or discontinuation from study treatment.

AEs that are related to a protocol-mandated intervention, including those that occur prior to assignment of study treatment (eg, screening invasive procedures such as biopsies).

An AE can arise from any use of the drugs (eg, off-label and in combination with another drug) and from any route of administration, formulation, or dose, including an overdose.

### 7.1.2 Progression of Underlying Malignancy

Progression of underlying malignancy should not be reported as an AE if it is clearly consistent with the suspected progression of the underlying cancer as defined by RECIST vI.1(solid tumor) or RANO

(glioma). Clinical symptoms of progression may be reported as AEs if the symptoms cannot be determined as exclusively due to the progression of the participant's underlying malignancy or does not fit the expected pattern of progression for the disease.

If there is any uncertainty about an AE being due only to the disease under study, it should be reported as an AE or SAE.

# 7.1.3 Hospitalization or Prolonged Hospitalization

Any AE that results in hospitalization or prolonged hospitalization should be documented and reported as an SAE except as outlined below.

The following hospitalization scenarios are **not considered** to be SAEs:

- Hospitalization for respite care
- Standard procedure for protocol therapy administration; however, hospitalization or prolonged hospitalization for a complication of therapy administration will be reported as an SAE
- Routine treatment or monitoring of the studied indication not associated with any deterioration in condition
- Administration of blood or platelet transfusion as routine treatment of studied indication; however, hospitalization or prolonged hospitalization for a complication of such transfusion remains a reportable SAE
- A procedure for protocol/disease-related investigations (eg, surgery, scans, endoscopy, sampling for laboratory tests, bone marrow sampling); however, hospitalization or prolonged hospitalization for a complication of such procedures remains a reportable SAE
- Hospitalization or prolongation of hospitalization for technical, practical, or social reasons, in absence of an AE.

